Appendix 11: SOP for urine Xpert MTB/RIF assay⁵

Materials

- Xpert DX System
- Xpert Instrument, computer, barcode reader
- Xpert MTB/Rif cartridge and sample reagent bottle
- Materials required but not provided in the kit
- Centrifuge
- Gloves
- Pipette (capable of dispensing 2mL)
- Biohazard disposable bags

Safety, Health & Environment

Treat all stool specimens as potentially infectious and follow basic universal precautions. Wear protective clothing (coat/apron and gloves) when handling the specimens.

Principle

The Xpert System integrates and automates sample processing, nucleic acid amplification, and detection of the target sequences using real-time PCR and reverse transcriptase PCR. The system requires the use of single-use disposable GeneXpert MTB/Rif cartridges that hold the PCR reagents and host the PCR process. Xpert MTB/RIF includes reagents for the detection of tuberculosis and RIF resistance as well as a sample processing control (SPC) to control for adequate processing of the target bacteria and to monitor the presence of inhibitor(s) in the PCR reaction. The Probe Check Control (PCC) verifies reagent rehydration, PCR tube filling in the cartridge, probe integrity, and dye stability. The primers in the Xpert MTB/RIF assay amplify a portion of the rpoB gene containing the 81 base pair “core” region. The probes are able to differentiate between the conserved wild-type sequence and mutations in the core region that are associated with RIF resistance.

Specimen collection and storage

Collect midstream urine in a fresh standard urine collection container. Fresh urine samples can be used within 3 hours if kept at room temperature.

Urine samples should be stored at 2-8°C if the test is to be run within 3 days of collection.

- If testing is delayed more than 3 days, the samples should be frozen (-20°C or colder). For frozen or refrigerated urine bring all samples to room temperature one hour prior to use. Frozen samples may contain aggregates.
- All thawed samples must be centrifuged at 3000 g for 15 minutes at room temperature. Specimens that have been frozen and thawed more than 3 times cannot be used.

Reagent storage and preparation

GeneXpert MTB/Rif cartridges must be stored at 2-28°C. Do not use beyond expiration date and do not open the cartridge until you are ready to perform the test (use the cartridge within 30minutes after opening its lid).

Test Procedure

- The sample of urine, 4ml, is centrifuged at 3000g for 5 minutes.
- Decant the supernatant and re-suspend the pellet/sediment in 2mL of the GeneXpert sample reagent.
- Thoroughly mix the re-suspension mixture, and add 2ml of the mixture into the GeneXpert MTB/Rif cartridge.
- Insert the cartridge into the GeneXpert instrument and proceed with testing (follow your laboratory Sop for operation of the GeneXpert Instrument).

Interpretation of test results:

- Interpret the results as you normally do with results from sputum samples processed in Xpert Instrument.
- The results are produced by the GeneXpert DX System from measured fluorescent signals and embedded calculation algorithms and will be displayed in the “View Results” window. Lower Ct values represent a higher starting concentration of DNA template; higher Ct values represent a lower concentration of DNA template.
- MTB Detected=> MTB target DNA is detected. The MTB result will be displayed as High, Medium, Low or Very Low depending on the Ct value of the MTB target present in the sample.
- RIF Resistance Detected=> will be displayed if the mutation in the rpoB gene has been detected. This is only displayed in MTB detected results.
- MTB Not Detected=>MTB target DNA is not detected

Quality control testing

Each GeneXpert test cartridge is a self-contained test device with an in-built control for each sample. Normally, no external controls are required. The internal controls enable the system to detect specific failure modes within each for each sample

- Instrument system control: Check status-it checks the optics, temperature of the module and the mechanical integrity of each cartridge. If the system controls fail, an ERROR test result will be reported.
- Probe Check control (PCC): after sample preparation, bead reconstitution and tube filling (prior to thermal cycling), multiple fluorescent readings are taken at different temperatures and compared to default setting. PCC controls for:
 - Missing target specific reagent (TSR) and or enzyme reagent beads which contain all primers, probes and internal control template.
 - Incomplete reagent reconstitution
 - Incomplete reaction tube filling
 - Probe degradation
- If the PCC fails, an ERROR test result will be reported.
- Sample processing control (SPC) assesses the effectiveness of the sample processing steps, including and up-to reaction tube filling. SPC ensures that the sample was correctly added to the cartridge and detects degradation of the enzyme(s) or other components of the system. SPC does not compete with target DNA.

- SPC must be Positive when target is Negative
 - SPC can be Positive or Negative when the target is Positive
 - SPC passes if it meets the validated acceptance criteria. E2097: too less sample volume added (<1mL), E2096: no sample added
- Internal Quantitative Standard High and Low (IQS-H and IQS-L): IQS-H and IQS-L are two dry bead armored RNAs nonspecific to HIV in the form of a dry bead that goes through the whole GX process. The IQS-H and IQS-L are standards calibrated against the WHO 3rd International Standard. They are used for quantification by using lot specific parameters for the calculation of HIV-1 RNA concentration in the sample. The IQS-H and IQS-L pass if they meet the validated acceptance criteria. They run internally with every cartridge and they control for reagent performance due to improper storage and they confirm that reaction components are set up correctly.
- External Controls: not available in the kit, but they can be used (positive and negative controls).

⁵ Based on OCB SOP Urine GeneXpert MTB/Rif Assay

Appendix 12: SOP for Xpert MTB/RIF assay performance

Xpert MTB/RIF assay is based on hemi-nested real time PCR for simultaneous detection of M. tuberculosis (MTB) and rifampicin (RIF) resistance. The target is the *rpoB* gene, critical for detection of mutations associated to rifampicin resistance. Xpert MTB/RIF automates all aspects of real time PCR analysis, with results available in 2 hours.

Sample processing

The test can be performed using fresh sputum samples or decontaminated samples prior culture inoculation.

Procedure with fresh sputum samples:

- Ask the patient to rinse the mouth twice before collecting the sample.
- Collect a minimum of 1.5 ml good quality sputum.
- Follow the procedures outlined below:

Procedure for Xpert MTB/RIF*

Step 1	Step 2	Step 3
 Add the reagent 2:1 (v/v) to the sample and shake 10-20 times. Incubate at room temperature for 15 min.; during incubation repeat once shaking for 10- 20 times.	 With a pipette transfer the diluted sample into a cartridge.	 Insert the cartridge in the machine and start the test.

* Source: National Health Laboratory Services, South Africa.

Procedure for sediment samples:

- Sediments can be prepared according to standard decontamination procedure (NALC-NaOH method) and re-suspend with phosphate buffer.
- Ensure 0.5 ml is available for the test; add 1.5 ml of reagent for 0.5 ml of re-suspended sediment.
- Follow the procedure described in the above figure.

Interpretation of the results:

Proper test performance is ensured by 2 internal controls:

- Sample processing control (SPC) ensures adequate processing and monitors presence of inhibition.
- Probe check control (PCC) verifies that the steps of the tests (rehydration, filling of the cartridge, etc.) take place correctly.

When the test is completed the display can show:

- “MTB detected” expressed by levels (the higher the level, the higher the amount of MTB detected in the sample) or “MTB not detected”;
- RIF results expressed as “detected”, “not detected” or “indeterminate” are available only if MTB is detected.

Other possible results:

- Invalid: MTB invalid and SPC failed due to one of several reasons, such as inhibition;
- Error: MTB no result, SPC no result, PCC failed; fail of system components;
- No result: e.g. tests stopped during processing.

Storage of samples and cartridges:

Samples:

- For a period \leq 3 days: store at 35°C maximum. A cold chain is not required for up to 3 days after collection. During this period of time, overgrowth of normal flora does not have negative influence on the test. However, if a cold chain is available, samples should be stored at 2 to 8°C in order to help their preservation.
- For a period of 4 to 10 days: store refrigerated at 2 to 8°C.

If samples require other testing (i.e. smear microscopy and/or culture), sample storing conditions adequate for microscopy and culture have to be followed. CPC does not interfere with Xpert MTB/RIF testing.

Cartridges:

- To be stored at 2 to 28°C.
- The cartridge should be used within 30 minutes of opening the cartridge lid.
- Cartridges are stable for 7 days after opening the packaging.

Logistic requirements

Power supply

- The device requires stable and uninterrupted power supply.
- Each GeneXpert instrument will need a uninterruptible power supply (UPS).
- The minimum requirement for the functioning of the GeneXpert instrument is to have a 800VA UPS.

Operating temperature

- The operating temperature for GeneXpert instrument device is 15 to 30°C. According to climate conditions, the installation of air conditioning can be recommended to keep the area within the temperature ranges indicated by the manufacturer.

Calibration

- The GeneXpert modules require annual calibration, which must be performed by an authorised service provider or carried out by swapping out the modules. A detailed commercial sales contract and customer support plan should be negotiated with the supplier, guaranteeing regular maintenance, calibration, repair and replacement (when needed).
- Cartridges and reagents shelf-life
- 12 months from date of production.

Storage space

- Each kit contains 10 cartridges and all reagents necessary to run 10 tests. The dimensions of the kit are 27 x 20 x 17 cm and the weight is 800 g.

Lab space

- The GeneXpert IV instrument (4 modules allowing the processing of 4 specimens at the same time) has the following dimensions:
- 29.8 cm wide, 35.6 cm high, 31.1 cm deep; weight: 12 kg. It is designed for indoor use only.
- Provide at least 5 cm of clearance on each side of the instrument to ensure adequate ventilation.
- Do not place the instrument close to the vents of other instruments or air-handling units.

Safety

- The personal protection requirements for microscopy should be adopted, including use of gloves and respirators.

Waste disposal

- Same procedure as for sputum containers. To be noted is the large volume of additional waste generated by Xpert MTB/RIF compared to smear microscopy.

Appendix 13: SOP for the diagnosis of HIV in children

[figure not shown]
1.1. Indication:

HIV infection should be systematically assessed in all children admitted to the ITFC ward and in children admitted to the Paediatric ward who present with clinical suspicion of HIV infection.

1.2. General principles:

- HIV testing should be performed by trained staff.
- HIV testing can only be performed after counselling and informed consent from the parents.
- In children under 5 years old, the mother will be tested first and the children will be tested only when:
 - Mother is HIV positive
 - Mother is negative but strong suspicion of HIV infection (ie. unsafe blood transfusion, traditional scarification or circumcision) or
 - In the absence of the mother
- HIV testing will be performed by using standard MSF (algorithm 1) or National testing algorithm.
- Children and/or mother with positive HIV diagnosis will be immediately linked to the HIV program, MSF supported or not.

1.3. Algorithm 1: MSF testing algorithm for mothers and children 18 months or more¹

[figure not shown]
¹ New HIV testing algorithm for MSF setting, October 2017

1.4. MSF testing for children under 18 months:

- In Guinea Bissau, all children under 18 months will undergo a PCR DNA.

For South Sudan:

- If child < 9 months and mother HIV positive or unknown: perform PCR DNA.
 - If child is 9 or more months but not yet 18 months, and mother positive or unknown: perform rapid test and confirm with PCR DNA if positive.
 - If child is 18 months and not breastfed in the last 6 weeks: follow algorithm 1.

Source WHO guidelines 2016 'Consolidated guidelines on the use of Antiretroviral drugs for treating and preventing HIV infection'

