0.6	369	189	93	64
0.7	323	165	81	56

With a precision of 12%, total number of 64 patients will be required to have a diagnosis of confirmed TB. If we assume that positivity of Xpert MTB/RR in sputum or validated extra pulmonary sample will be 20% (rate non-sick/sick = 4), we will need a total of 320 suspected TB patients will be needed (160 per project) to achieve 64 patients with confirmed TB (32 per project). We assume that 2% of the children won't be capable of producing stools, therefore the final sample size will be 327.

e. Definitions

1. SAM (severe acute malnutrition) in children:

- Children < 5 years old: Z-score weight / height <-3 and / or MUAC <11.5 cm, and / or bilateral oedema.
- Children 5-15 years old: weight for height < 70% (see table in Appendix 16) or bilateral oedema

2. HIV infection:

All patients with suspected TB will be tested for HIV, after consent of the legal responsible and pre-test counselling. The algorithm test will be adjusted to the age of the child (see Appendix 12). All children < 18 months will need PCR DNA for HIV diagnosis. All children ≥ 18 months and > 6 weeks of breastfeeding cessation will follow same diagnostic algorithm as for adults, which requires 3 positive rapid tests.

3. Suspected case of tuberculosis (40,41):

Any child with at least one of the following signs, symptoms or features is considered a **suspected case of tuberculosis** (Appendix 4):

- Persistent cough for more than 2 weeks
- Unexplained fever for more than a week
- Suspected extra-pulmonary tuberculosis (TBEP), e.g.:
 - Angular deformation of the spine (gibbous)
 - Lymphadenopathy
 - Subacute meningitis
 - Abdomen distended with ascites

- > 2 weeks of diarrhoea
- Painless enlarged joints
- Pleural effusion
- Other

All **HIV positive** and **SAM children**, as well as all **TB contacts**, will systematically and actively be screened for TB.

Tuberculosis screening in children is done on admission and during hospitalization. If children are not identified as suspected TB cases at admission, a new assessment will be done after 1 week of admission. In addition to the above criteria, tuberculosis is suspected based on the following signs, symptoms and characteristics during hospitalization:

- Low weight gain despite correct nutritional treatment
- Persistent pneumonia after adequate and well-followed antibiotic therapy
- Persistence of cough

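### Section 7.e.2 and Appendix 5 have every suspected child tested for HIV, Appendix 13 does not, and nothing says which governs, so the HIV strata rest on an undefined ascertainment rule

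*Combined protocol and SAP*

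**What the plan says.** Section 7.e.2 (HIV infection) is unconditional on who is tested: "All patients with suspected TB will be tested for HIV, after consent of the legal responsible and pre-test counselling". For the youngest it adds: "All children < 18 months will need PCR DNA for HIV diagnosis". It says the algorithm depends on age and sends the reader to Appendix 12. Appendix 5, note c, includes HIV testing in the comprehensive assessment if not already done, with no ward or maternal condition, and sends the reader to Appendix 16.

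The SOP itself is Appendix 13. Appendix 12 covers Xpert assay performance, and Appendix 16 holds the weight-for-height tables. Appendix 13 says:

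- **Indication (1.1):** systematic assessment of all ITFC admissions and of "children admitted to the Paediatric ward who present with clinical suspicion of HIV infection". OPD and PICU are not mentioned, although section 8.a lists both as places where participants are identified.
- **General principles (1.2):** "In children under 5 years old, the mother will be tested first and the children will be tested only when" the mother is HIV positive, the mother is absent, or the mother is negative but suspicion is strong. The choice between the MSF and the national algorithm is left open.
- **Under 18 months (1.4):** "In Guinea Bissau, all children under 18 months will undergo a PCR DNA". For South Sudan, a test is listed only if the mother is positive or of unknown status: PCR below 9 months, and from 9 months "perform rapid test and confirm with PCR DNA if positive".

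HIV status is used in three places. Secondary objective 2 splits accuracy into HIV positive and negative. Secondary objective 3 describes LAM positivity by HIV status. Section 7.e.4 counts a positive LAM as confirmed TB only in HIV-infected children.

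**The concern.** Staff cannot follow both texts for the same child. If Appendix 13 is followed, some participants will have no HIV test of their own. Who they are will depend on the ward they came through, whether a clinician suspected HIV, the mother's result and the country. A comparison of stool or urine Xpert between HIV strata could then mix test performance with the way HIV status was obtained.

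The data could not be separated afterwards. The clinical CRF (Appendix 4) allows negative, positive and unknown, plus two PCR-pending boxes, but has no field for the basis of the status. The lab CRF (Appendix 17) has no HIV entry. An untested child of an HIV-negative mother could be entered as negative by one clinician and unknown by another. Section 10 does not say how unknown or pending status enters a positive/negative split.

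**Working it through.** **1. The texts side by side.** Cases that the rules treat differently:

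| Child with suspected TB | Section 7.e.2 | Appendix 13 |
|---|---|---|
| 18 months to under 5 years, ITFC, mother negative, no strong suspicion | Tested | Mother tested, child not (1.2) |
| 5 years or over, paediatric ward, no clinical suspicion of HIV | Tested | Systematic assessment not called for (1.1) |
| Any age, OPD or PICU | Tested | Not mentioned (1.1) |
| 9 to under 18 months, Malakal, mother unknown | PCR | Rapid test, PCR only if positive (1.4) |
| Under 18 months, Malakal, mother negative | PCR | No test listed (1.4) |
| Under 18 months, Bissau, mother negative, no strong suspicion | PCR | Not tested by 1.2, PCR by 1.4 |

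The last row shows Appendix 13 contradicting itself. The two rows for Malakal infants, set against the Bissau row, show that ascertainment under 18 months differs by site.

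**2. Does it touch the sample size?** No. The plan's figures reproduce without any HIV input (95% two-sided confidence assumed, since the section gives none):

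- n = 1.96² × 0.60 × 0.40 / 0.12² = 64.02, stated as 64 confirmed cases.
- 64 / 0.20 = 320 suspected cases; 320 / 0.98 = 326.5, so 327.
- 143 (Malakal) + 184 (Bissau) = 327.

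**3. Scale of the HIV-positive stratum.** This is an illustration, not an estimate. Section 5 gives HIV co-infection of 11% for Malakal and 32% for TB patients in Guinea Bissau. Neither is specific to children; applying them to confirmed paediatric cases is an assumption.

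- Malakal: 143 × 0.98 × 0.20 = 28.0 confirmed; × 0.11 = 3.1 HIV-positive.
- Bissau: 184 × 0.98 × 0.20 = 36.1 confirmed; × 0.32 = 11.5 HIV-positive.
- Total: 14.6, about 15.

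At 60% sensitivity the half-width for 15 children is 1.96 × √(0.24 / 15) = 0.248, about 25 points. The exact 95% interval for 9/15 is 32% to 84%.

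**4. Range for missed infections.** The documents give no rate. If 10% to 50% of infected confirmed cases were missed (assumed):

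- Malakal only: 3.08 × 0.10 = 0.3 to 3.08 × 0.50 = 1.5 children leave the HIV-positive stratum.
- Both sites: 14.62 × 0.10 = 1.5 to 14.62 × 0.50 = 7.3 children.

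The range is wide because nothing in the plan narrows it. The mother-first rule alone leaves untested only children whose mother is negative and in whom suspicion is not strong, which argues against the upper end for that rule. The ward rule has no such limit.

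**The case against.** The strongest reply is that universal testing is stated twice, in section 7.e.2 and Appendix 5, while Appendix 13 carries no asterisk and so is not specific to this study. On that reading every participant is tested. Section 1.1 of Appendix 13 also says where systematic assessment should happen and does not forbid testing elsewhere. This has weight: large numbers of children with unknown status follow only if Appendix 13 prevails. It does not settle the matter. The missing asterisk means that the appendix is shared with the POCUS study, not that it is inapplicable here; it is the only HIV SOP and the evident target of both misnumbered references.

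Second, variation by age is planned, and the PCR sentence in section 7.e.2 may mean that PCR is needed to establish infection. That would ease the conflict at 9 to under 18 months in South Sudan, where a positive rapid test is confirmed by PCR. It leaves the conflict over who is tested. The algorithm figures are not shown and cannot be judged.

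Third, the CRF already records unknown and PCR-pending status. True, but it does not separate a child's own negative result from one inferred from the mother.

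A reader might also infer that these rules make the LAM part of the reference standard non-comparable between sites. The documents do not support that. LAM is planned only in Malakal, from November 2021 (section 8.b.2), after the July 2021 end of the timeframe in the Summary, so Bissau has no study LAM result under any HIV rule. The comparator in the main objective (section 6.a) does not name LAM either. The HIV rules bear only on which Malakal LAM positives count as confirmed.

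**Conclusion.** The inconsistency is real and should be resolved. Section 7.e.2 and Appendix 5 conflict with Appendix 13 on who is tested; section 7.e.2 also conflicts with it on the test used under 18 months; and Appendix 13 conflicts with itself for Bissau. As written, the plan does not secure that HIV status is obtained in the same way across wards and sites.

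The consequence is limited to the HIV strata of secondary objectives 2 and 3 and the classification of Malakal LAM positives. It would reach the primary comparison only if LAM belongs to the primary reference standard, which sections 6.a and 7.e.4 leave unclear. The sample size does not change.

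Two stronger readings should be resisted. The strata are not shown to be non-comparable: that depends on Appendix 13 being the text followed. Nor can a percentage misclassified be attached: the co-infection rates are not child-specific, no missed-infection rate is given, and the under-5 share of children treated in Malakal in 2017 is not the share left untested. With about 15 HIV-positive confirmed cases under the stated assumption, that stratum is already imprecise, and a few misplaced children would matter most there.

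**What to change.** - Reconcile section 7.e.2, Appendix 5 and Appendix 13 so that one stated testing rule applies to study participants at each site. Which rule is clinically right is not for this review.
- Correct the cross-references to the HIV SOP in section 7.e.2 and Appendix 5.
- Add a CRF field for the basis of HIV status: child PCR, child rapid test, inferred from mother, not tested.
- State in section 10 how unknown and pending status are handled. Report the HIV strata by site, with inferred and unknown status in separate rows.
- Show results both with and without inferred-negative children. A tested-only stratum is not a neutral default: under Appendix 13, tested under-5s are largely those with a positive or absent mother or strong suspicion, so their HIV-negative group would itself be selected.

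The cost is wording changes, one CRF field, a few table rows and smaller strata. For children already enrolled, the basis of status can be filled in only where source records show it; otherwise they belong in the unknown row.
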